7.1. Inclusion criteria

- 1) coronary artery disease including in-stent restenosis (ISR) or de novo lesion with stenosis of $\geq 70\%$,
- 2) target lesion calcification confirmed by an imaging study: various degrees of calcium deposition along the coronary artery wall (an arch of calcium at least 100 degrees) confirmed at baseline coronary angiography, computed tomography, and IVUS),
- 3) reference vessel diameter between 2.0 and 4.0 mm, deemed suitable for percutaneous coronary intervention (PCI).

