[figure not shown]

Study Title	
Assessment of Cutting-Balloon Angioplasty with Novel Bioabsorbable Polymer-Coated, Everolimus-Eluting Stent in the Treatment of Calcified Coronary Lesions Guided by Intravascular Ultrasound: Study Design and Protocol

Study Title (Short Description)	
CUPID trial

Principle Investigator	
[name]., PhD.

Institution Name & Location	
SoonChunHyang University Hospital [name]

Contact information	
Email: [contact] [contact] [contact]

1. Study protocol

Novel cutting balloon prospective, randomized, open-label, multi-center study

This clinical trial is designed as a prospective, observational, open-label, multi-center trial that will investigate the noninferiority of cutting balloon pre-dilatation compared with NC-balloon pre-dilatation in the treatment of calcified lesion who underwent bioabsorbable polymer-coated, everolimus-eluting coronary stent implantation.

Planned number of sites: 5 institutions in South Korea

1. SoonChunHyang University Hospital, Bucheon
2. SoonChunHyang University Hospital, Cheonan
3. Eulji Medical Center, Eulji University, Daejeon
4. Seoul St.Mary's Hospital, Seoul
5. Hanil General Hospital, Seoul

2. Study Outcomes

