5.2. Secondary endpoint: comparing the clinical outcomes

- ① MACE (major adverse cardiac events): composite of death, MI, TVR at 1yr follow-up
- ② TLR (target lesion revascularization) at 1yr follow-up
- ③ Procedure time, the total amount of contrast, and the number of balloons

3. Analysis plan

- 6.1. Study period: 24 months
- 6.2. Enrollment: 12 months
- 6.3. Follow-up: 12 months
- 6.4. Analysis and result report: 2 months

4. Sample size calculation for the primary analysis

4.1. Hypothesis:

This trial is a 1:1 matched comparative cohort clinical trial, with patients being assigned to either the cutting balloon or the NC balloon group (1: 1 ratio) during the study period. It will test the noninferiority of a strategy of cutting balloon pre-dilatation compared with NC balloon pre-dilatation in the treatment of calcified coronary lesion. minimal CSA at the calcium site assessed by IVUS is the primary endpoint. Limited similar clinical trials on cutting balloon for the treatment of de novo various degree calcified coronary lesions have achieved differing results. The result of a previous study that investigates the efficacy of cutting balloon indicates that the mean CSA after cutting balloon treatment for native coronary artery disease are 6.26mm and 5.03 mm in the NC balloon group (18). We hypothesize that stent implantation after the cutting balloon pre-dilatation will not be inferior to pre-dilatation with NC balloon for the treatment of de novo calcified coronary lesions. Using double-sided inspection, $\alpha = 0.05$ and $\beta = 0.2$, and considering the expected loss to follow-up of 20%, the number of cases to be included should be at least 250. Therefore, we aim for 125 cases for each group. Nevertheless, the sample size proposed was 250 patients in each group to further increase the power and account for possible protocol deviation.

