4.2. Assumption

Data for all endpoints will be evaluated using an intention-to-treat analysis. All data will be expressed as mean \pm standard deviation. The unpaired Student's t-test and Mann-Whitney U test will be used to compare continuous variables. Categorical variables will be compared using the chi-square and Fisher's exact tests. All time-to-event outcomes of MACEs will be summarized using Kaplan-Meier survival estimates and compared between the two groups using log-rank tests. $p < 0.05$ is considered statistically significant. All statistical analyses will be performed using SPSS software (version 20.0, SPSS Inc., Chicago, IL, USA).

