Coronary angiography will be digitally recorded at baseline and immediately after the procedure (post-balloon and post-stenting) and assessed offline in the angiographic core laboratory. The quantitative coronary angiographic analysis will be performed using an automated edge-detection algorithm (CAAS-5; Pie-Medical, Best, Netherlands) with conventional methods by independent interventional cardiologists who are blinded to the type of balloon used, treatment outcomes, and IVUS analysis. All measurements will be performed using cineangiograms recorded after the intracoronary injection of nitroglycerin. The interpolated reference diameter will be considered as the reference segment diameter. The lesion length is defined as the distance from the proximal shoulder to the distal shoulder at the lesion site. Standard qualitative and quantitative analyses and definitions will be used for quantitative coronary angiography (QCA) (qca 1, 2 references).

5.3. IVUS procedure and analysis:

After regular coronary angiography, IVUS will be performed at baseline (before pre-dilatation) and repeated immediately after stent implantation in all cases. IVUS will be performed using an OptiCross 60 MHz (Scientific Corporation, Maple Grove, MN, USA). After intracoronary injection of nitroglycerin, the IVUS catheter will be carefully advanced distal to the culprit lesion under fluoroscopic guidance and then withdrawn automatically at 0.5 mm/s to perform the imaging sequence, which begins 20 mm distal to the culprit lesion and ends at the aorto-

ostial junction. IVUS imaging will be recorded on the compact disc for offline analysis by a single experienced observer who is unaware of the clinical and angiographic information. IVUS measurements will be performed in accordance with the American College of Cardiology Clinical Expert Consensus Document on the Standards for Acquisition, Measurement, and Reporting of Intravascular Ultrasound Studies. The ischemia-related vessel is identified as narrow ($\geq 70\%$) using angiography. The culprit lesion site selected for analysis is the image slice with the lowest luminal cross-sectional area (CSA). The proximal and the distal reference segments are defined as the most normal-looking cross-sections within the same arterial segment, typically ≤ 10 mm from the lesion, but before any large side branch.

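### The noninferiority claim is stated for calcified lesions generally in two places and for de novo lesions only in a third; in-stent restenosis is eligible, and no planned analysis isolates de novo lesions

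*Combined protocol and SAP*

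**What the plan says.** The aim appears three times, with two different scopes.

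- **Section 1 (Study protocol):** noninferiority of cutting-balloon pre-dilatation "compared with NC-balloon pre-dilatation in the treatment of calcified lesion who underwent" stenting. There is no de novo limit.
- **Section 4.1 (Hypothesis), statement of what the trial will test:** noninferiority of the cutting-balloon strategy "compared with NC balloon pre-dilatation in the treatment of calcified coronary lesion". Again there is no de novo limit.
- **Section 4.1, hypothesis sentence:** stenting after the cutting balloon will not be inferior to "pre-dilatation with NC balloon for the treatment of de novo calcified coronary lesions". This one is limited to de novo lesions.

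Section 4.1 also describes the earlier trials as concerning de novo lesions, and it takes its planning values from a study in which "mean CSA after cutting balloon treatment for native coronary artery disease are 6.26mm and 5.03 mm in the NC balloon group".

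On who is enrolled, inclusion criterion 1 (Section 7.1) reads "coronary artery disease including in-stent restenosis (ISR) or de novo lesion with stenosis of" at least 70%. The exclusion list in Section 7.2 removes vein-graft lesions but not ISR.

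On analysis, Section 4.2 states: "Data for all endpoints will be evaluated using an intention-to-treat analysis". The unpaired Student's "t-test and Mann-Whitney U test will be used to compare continuous variables". No section defines a de novo analysis set, a stratum or covariate for lesion type, a limit on ISR enrolment, or a separate estimate for either lesion type.

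**The concern.** A noninferiority conclusion belongs to a population, and here the text supports two. If the broader wording governs, the planned intention-to-treat comparison is aimed at the right patients. If the hypothesis sentence governs, the comparison mixes in patients whom the hypothesis does not mention, and nothing in the plan recovers the de novo result.

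What is at stake is the wording of the conclusion. If the question is left open until the data are seen, a report could claim de novo noninferiority from a pooled estimate, or choose the population that gives the cleaner result. An ISR lesion already contains a stent, so equal balloon effects on minimal stent cross-sectional area (CSA) in the two lesion types should not be assumed silently.

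**Working it through.** **Inputs.** From the documents: planning means 6.26 and 5.03, two-sided alpha 0.05, 80% power and 20% loss (Section 4.1); 125 per arm (Section 4.3). Section 4.1 also mentions 250 in each group, so that case is shown as well. Not in the documents, and therefore assumed: ISR share *f* of 10, 20 or 30%; effect difference *D* (ISR effect minus de novo effect) of 0.5 or 1.23 in size; SD of 2.0 or 3.1.

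**Step 1: the plan's own figure.** The total of 250 cannot be reproduced, because neither an SD nor a noninferiority margin is given. The planning difference is 6.26 − 5.03 = 1.23. Read as a superiority calculation, n per arm = 2 × SD² × (1.960 + 0.842)² / 1.23². With SD = 3.10 this is 2 × 9.61 × 7.85 / 1.513 ≈ 100, and 100 / 0.8 = 125. The SD of 3.1 used below is back-solved in this way. It is not a stated value, and it comes from a superiority formula although the trial is described as noninferiority.

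**Step 2: fit of the analysis to each statement of the aim.** Intention-to-treat over patients who meet Section 7.1 means all eligible calcified lesions, ISR included. That matches Section 1 and the first of the two statements in Section 4.1. It does not match the hypothesis sentence.

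**Step 3: how far the pooled effect can lie from the de novo effect.** With the same ISR share in both arms,

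pooled = (1 − f) × de novo effect + f × ISR effect, so pooled − de novo = f × D.

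| Size of D | f = 10% | f = 20% | f = 30% |
|---|---|---|---|
| 0 | 0 | 0 | 0 |
| 0.5 | 0.05 | 0.10 | 0.15 |
| 1.23 | 0.12 | 0.25 | 0.37 |

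The value 1.23 is only a yardstick, the size of the planning difference.

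**Step 4: which direction matters.** Let a positive effect favour the cutting balloon.

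- If D ≤ 0 (ISR effect no better than de novo), the pooled effect is at or below the de novo effect, so a noninferior pooled effect is conservative for de novo lesions. Example: de novo effect 1.23 and ISR effect 0 at 30% ISR give 1.23 − 0.369 = 0.86, still in favour of the cutting balloon.
- If D > 0, the pooled effect overstates the de novo effect by f × D. The true de novo effect could then lie beyond the margin while the pooled effect lies inside it. With no margin stated, the shift cannot be judged against one.

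**Step 5: precision of separate estimates.** IVUS is "repeated immediately after stent implantation in all cases" (Section 5.3), so loss during the one-year follow-up does not by itself remove the primary endpoint, and 125 per arm is used. The 95% CI half-width is t × SD × √(2/n). For the difference in effect, √(2/n) is replaced by √(2/n_de novo + 2/n_ISR).

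| ISR share | 10% | 20% | 30% |
|---|---|---|---|
| De novo / ISR n per arm | 113 / 12 | 100 / 25 | 88 / 37 |
| De novo width relative to pooled, 1/√(1 − f) | 1.05 | 1.12 | 1.20 |
| De novo half-width, SD 2.0 / 3.1 | 0.52 / 0.81 | 0.56 / 0.86 | 0.60 / 0.92 |
| ISR half-width, SD 2.0 / 3.1 | 1.69 / 2.62 | 1.14 / 1.76 | 0.93 / 1.44 |
| ISR-minus-de novo half-width, SD 2.0 / 3.1 | 1.69 / 2.62 | 1.25 / 1.93 | 1.09 / 1.69 |

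The pooled half-width is 0.50 (SD 2.0) or 0.77 (SD 3.1). At 250 per arm, the ISR half-widths become 1.14, 0.79 and 0.65 (SD 2.0) or 1.76, 1.23 and 1.00 (SD 3.1).

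**The case against.** The strongest reply is that two of the three statements of the aim already fit the enrolled population. Intention-to-treat over eligible patients defines that population clearly, and one narrower sentence is a drafting slip. Much of this stands. A reader might infer that the primary analysis fails to test the trial's hypothesis. The documents do not support that, because the analysis does test the aim as worded in Section 1 and in the other sentence of Section 4.1. What remains is that the narrower sentence is the formal hypothesis, that the same section frames the earlier trials as de novo, and that nothing says which wording governs.

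Two further inferences are tempting and should be resisted.

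- **That the planning means exclude ISR.** The protocol calls the source native coronary artery disease. Native can also be contrasted with bypass grafts, and the documents do not show whether that study enrolled ISR.
- **That the pooled result answers the de novo question only if the effects are equal.** This is too strong. Few or no ISR patients, or an ISR effect no better than the de novo effect, leaves the de novo conclusion intact or conservative.

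It is also fair to object that a lesion-type covariate does not cure the mismatch. An adjusted comparison still gives one effect across both lesion types. Its justification is precision and protection against imbalance. The second matters because Section 1 calls the trial both randomized and observational, and Section 4.1 calls it a matched cohort.

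**Conclusion.** The inconsistency is real and can be read directly from the text: the planned primary analysis serves the broader aim, and no planned analysis isolates the de novo hypothesis. Its numerical effect is unknown, because the ISR share, the effect in ISR, the SD and the margin are all absent. Under the assumed values the shift is 0.05–0.37, and it is zero if the effects are equal. It threatens the de novo noninferiority conclusion only when the cutting balloon does relatively better in ISR.

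A reader might take this as a forecast of lost power or a failed trial. The documents do not support that, since noninferiority power cannot be computed without a margin. The point concerns which population the conclusion covers, and it should be settled before analysis.

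**What to change.** Before analysis:

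1. Reconcile Sections 1, 4.1 and 7.1 by stating one confirmatory noninferiority hypothesis for all eligible calcified lesions, ISR included, and say in Section 4.2 that it is tested in the intention-to-treat set.
2. Prespecify the de novo difference in minimal stent CSA, with its confidence interval, as a supporting and non-confirmatory estimate. Report the ISR difference with its interval as descriptive.
3. Adjust the primary comparison for lesion type (ISR or de novo, known at eligibility), and state that this is for precision and protection against imbalance, not a remedy for the population mismatch.

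**Cost.** Text edits, one degree of freedom and two extra estimates, with no change to eligibility or enrolment. The de novo interval is about 5–20% wider than the pooled one at an assumed 10–30% ISR. The ISR estimate is imprecise: at 125 per arm its half-width is about 0.9–1.7 at SD 2.0 and 1.4–2.6 at the back-solved SD of 3.1, larger than any shift illustrated above. The separate estimates show the result by lesion type but cannot confirm that the effects are equal.

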7.2. Exclusion criteria

- 1) extremely tortuous or angulated lesions,
- 2) lesions with dissection before balloon pre-dilatation,
- 3) lesions within the vein graft,
- 4) extremely narrow lesions which need rotational atherectomy,
- 5) ST-elevation myocardial infarction (STEMI).
- 6) Comorbidities that preclude the achievement of one-year follow-up.

8. Expected study period

- Enrollment: 12 months
- Follow-up: 12 months
- Data analysis: 2 months
- Publication including target journal and presentation:
JACC: Cardiovascular Interventions
Circulation: Cardiovascular Interventions
TCT 2025

9. Safety Reporting including DSMB

9.1. Potential risk and adequacy of protection against risks

In patients undergoing intervention and revascularization, treatment decisions should be based on clinical indication, regardless of sex, or race or ethnicity, and efforts to reduce the disparities of care are warranted. In patients undergoing revascularization, decision should be patient-centered *that is, considerate of the patient's preferences and goals, cultural beliefs, health literacy, and social determinants of health* and made in collaboration with the patient's support system. In patients undergoing coronary angiography and revascularization, adequate information benefits, risks, therapeutic consequences, and potential alternatives in the performance of percutaneous and surgical myocardial revascularization, when feasible, with sufficient time for informed decision-making to improve clinical outcomes.

9.2. Event adjudication and reporting, data safety and monitoring plan

1) Data safety and monitoring plan

The principal investigator will make the monitoring manager to visit and examine coordinating centers regularly. A designated trial monitor will review data not only for completeness, but also for accordance of the hospital data and eCRF data. Compliance with the protocol and adverse events will be also examined. This trial monitor may inspect all documents and required records that are maintained by the Investigator/site, including medical records (office, clinic, or hospital) for the subjects in this trial. The coordinating centers will permit access to such records.

Type of Report	Prepared by Staffs for:	Time limit of notification
Serious adverse event	IRB	According to IRB regulation of Site
	DCC/EC/Principal investigator DSMB	Within 48 hours
Annual progress report	EC/Principal investigator	Submitted per 1 year
Deviations from investigational plan	IRB	According to IRB regulation of Site
	EC/Principal investigator	Notify within 7 days.

Final summary report	EC/Principal investigator	Within 1 month
----------------------	---------------------------	----------------

*DCC: Data Coordinating Center, EC: Executive Committee (Co-researchers)

2) Executive Committee

	Name	Center	Position
Chairman	[name]	Department of Cardiology, SoonChunHyang University Bucheon Hospital, SoonChunHyang University College of [name].
Committee members	[name]	Department of Cardiology, SoonChunHyang University Cheonan Hospital, SoonChunHyang University College of [name]
	[name]	Department of Internal Medicine, Daejeon Eulji Medical Center, Eulji University School of [name]
	[name]	Department of Cardiology, Hanil General Hospital, [name]
	[name]	Department of Cardiology, SoonChunHyang University Bucheon Hospital, SoonChunHyang University College of [name]
	[name]	Department of Cardiology, Seoul St. Mary's Hospital, The Catholic University of [name]
	[name]	Department of Cardiology, SoonChunHyang University Bucheon Hospital, SoonChunHyang University College of Medicine	MD.

3) Serious Adverse Events

The definition of serious adverse events is in the following paragraph. It must be reported to the principal investigator within 48hours after recognition of the event and to the IRB according to IRB regulation of site.

- ① Results in persistent or significant disability or incapacity (significant, persistent or permanent change or disruption in subject's body function/structure, physical activity or quality of life)
- ② Requires in-patient hospitalization or prolongs hospitalization
- ③ Results in a congenital anomaly/birth defect or,
- ④ Life-threatening events or death

4) Event adjudication committee

	Name	Center	Position
Chairman	[name]	Cardiovascular Center, Dongguk University Ilsan Hospital, [name]

		University	
Committee members	[name]	Division of Cardiology, Department of Internal Medicine, Hanyang University Guri [name]
	[name]	Department of Cardiology, Sejong General Hospital, Bucheon	MD.

5) Data safety and monitoring board

	Name	Center	Position
Chairman	[name]	Department of Cardiology, Yongin Severance Hospital, Yonsei University College of [name]
Committee members	[name]	Department of Microbiology and BK21 FOUR Project, SoonChunHyang University College of Medicine,	PhD.
	[name]	Department of Cardiology, SoonChunHyang University Bucheon Hospital, SoonChunHyang University College of Medicine	MD

The DSMB reviews the safety data and delivers recommendations for it. The DSMB may convene a meeting at any time if it deems that there is a safety problem.

The DSMB Charter is drafted before the DSMB's first data review. The plan defines its regulations when clinical trials are suspended due to safety concerns. At the first meeting of the DSMB, understanding and discussion of all elements of the plan and determination of the frequency of DSMB meetings are made. DSMB develops an understanding of all evaluation variables in this clinical trial and all definitions used in the judgment.

The Commissioners do not directly coordinate the client of this clinical trial. The committee members have no interest in the central analysis room or with the researchers of this clinical trial. The configuration of the DSMB includes at least two cardiovascular intervention specialists. The names of the actual members are not published and can be provided to regulators as needed. DSMB functions in accordance with relevant regulations.

The DSMB Chairman shall notify the DCC if he deems that there is a problem with safety or compliance with the plan. The Commission may, if necessary, recommend an early suspension in accordance with the safety-related early discontinuation principle determined prior to the start of a clinical trial, or if clinically significant results are found in the safety-related data. All DSMB reports must be strictly confidential and provided at the request of regulators.
